6.1.6 ROUTE OF ADMINISTRATION

Lenvatinib, Sorafenib, Cabozantinib, and Vandetanib will be taken orally.

6.1.7 STARTING DOSE AND DOSE ESCALATION SCHEDULE

The starting dose of Lenvatinib in patients with DTC is 24 mg/day. This is the maximal dose that study participants will receive.

The starting dose of Sorafenib in patients with DTC is 400 mg twice daily. This is the maximal dose that study participants will receive.

The starting dose of Cabozantinib in patients with MTC is 140 mg/day. This is the maximal dose that study participants will receive. Patients with hepatic impairment will start treatment at 80 mg/day.

The starting dose of Vandetanib in patients with MTC is 300 mg/day. This is the maximal dose

that study participants will receive.

6.1.8 DOSE ADJUSTMENTS/MODIFICATIONS/DELAYS

All patients will start receiving standard of care treatment:

- DTC: Lenvatinib 24 mg daily or Sorafenib 400 mg twice daily
- MTC: Cabozantinib 140 mg daily or Vandetanib 300 mg daily.

Dose will be adjusted as needed due to toxicity or drug tolerance in both arms (See below).

- Patients in the conventional therapy regimen (“responders” and non-responders”) will receive continuous (daily) treatment at the indicated dose.

- Patients in the adaptive therapy regimen will receive TKI therapy in cycles: continuous (daily) treatment at the indicated dose until the patients’ tumor marker (thyroglobulin in DTC patients; calcitonin or CEA in MTC patients) drops by $\geq 50\%$ from the level at the time of enrollment (“baseline” level). Only tumor markers that meet inclusion criteria at baseline can be used for randomization and adaptive therapy purposes. A new cycle of TKI treatment will begin:

1. When/if the tumor marker increases to $\geq 70\%$ of the “baseline” level.

OR

2. At the discretion of the treating physician if a patient develops worsening disease-related symptoms with rising tumor marker levels indicating disease progression. In the case of resumption for disease-related symptoms, TKI treatment will continue until the symptoms improve at the discretion of the treating physician and the tumor markers are again $\leq 50\%$ from the level at the time of enrollment.

All study participants will continue to receive treatment until confirmed disease progression, development of unacceptable toxicity, withdrawal of consent, or study termination by investigator.

After disease progression subjects will be followed for survival and may be treated according to standards of care, which includes conventional (continuous) TKI treatment for patients in the adaptive therapy arm.

Held doses will be considered missed and will not be made up so that patients will complete on-study treatment within the anticipated 24 month duration. Treatment may be delayed for toxicity, other palliative treatments (i.e. palliative radiation, palliative surgery, etc.) for a maximum of 4 weeks. Any treatment beyond the 24 months specified herein will be considered off protocol and not subject to the requirements of this protocol.

6.1.8.1 MANAGEMENT OF MOST COMMON GENERAL SIDE EFFECTS OF TKI TREATMENT (NOT AGENT-SPECIFIC)

MANAGEMENT OF HYPERTENSION

- Insure BP $\leq 150/90$ mmHg at the time of study entry.
- Discuss preventive measurements.
- Insure that study participants has a BP cuff at home and are willing to measure BP twice a day and report if elevated.

- Patients will be asked to maintain a diary of these measurements to be reviewed with the treating physician or APP during clinic visits
- If patient reports 3 consecutive at-home systolic BP measurements of ≥ 140 mmHg and/or diastolic BP measurements of ≥ 90 mmHg, they will be instructed to set up a clinic visit to be assessed for further management. The BP measurements obtained in clinic will be used to manage hypertension as detailed further below.
- Treat SBP ≥ 140 mmHg and/or DBP ≥ 90 mmHg with antihypertensive agents individualized to the subject's clinical circumstances based on standards of clinical practice.
- For subjects with hypertension and proteinuria, treatment with an angiotensin-converting enzyme inhibitor or angiotensin-II receptor antagonist is preferred.
- TKI should be withheld in any instances where a subject is at imminent risk to develop a hypertensive crisis or has significant risk factors for severe complications of uncontrolled hypertension (e.g., BP $\geq 160/100$ mmHg, significant risk factors for cardiac disease, intracerebral hemorrhage, or other significant co-morbidities). Once the blood pressure is controlled, study drug should be resumed as described below.
- If systolic BP ≥ 160 mmHg or diastolic BP ≥ 100 mmHg persists despite maximal antihypertensive therapy, then study drug administration should be interrupted and restarted at a dose of 20 mg once daily when BP $\leq 150/95$ mmHg.
- If systolic BP ≥ 160 mmHg or diastolic BP ≥ 100 mmHg recurs on the 20-mg once daily dose despite optimal management of hypertension with antihypertensive medications (either by dose increase or the addition of a different class of antihypertensive), then study drug administration should be interrupted and restarted at a dose of 14 mg once daily when BP $\leq 150/95$ mmHg.
- If systolic BP ≥ 160 mmHg or diastolic BP ≥ 100 mmHg recurs on the 14-mg once daily dose despite optimal management of hypertension with antihypertensive medications (either by dose increase or the addition of a different class of antihypertensive), then study drug administration should be interrupted and restarted at a dose of 10 mg once daily when BP $\leq 150/95$ mmHg.
- For Grade 4 hypertension (life-threatening consequences) discontinue study drug.
- Additional dose reduction should be upon medical judgment of PI.

MANAGEMENT OF PROTEINURIA

- Regular assessment for proteinuria should be conducted as specified in study calendar (See Table 8).
- Initial episode of proteinuria: if proteinuria $\geq 2+$ is detected on urine dipstick testing study drug will be continued and a 24-hour urine collection for total protein will be obtained as soon as possible within 72 hours to verify the grade of proteinuria. Withhold TKI for ≥ 2 grams of proteinuria/24 hours and resume at a reduced dose when proteinuria is < 2 grams/24 hours.
- Discontinue TKI for nephrotic syndrome

MANAGEMENT OF DIARRHEA

- Diarrhea is very common with TKIs. The first step in management of diarrhea, however, is to investigate other potential causes including: other medications such as laxatives, stool softeners or antibiotics; lifestyle factors such as excessive dietary fiber or lactose; and infectious causes of diarrhea.
- TKI related diarrhea is usually mild to moderate and early management is essential to prevent dose reduction or discontinuation. Antimotility agents such as loperamide should be initiated on appearance of mild diarrhea, and patients should avoid foods that cause symptoms. Patients should be advised to drink approximately three liters of liquids a day to

minimize the risk of dehydration.

- If diarrhea persists despite up to 20 mg loperamide per day, patients should return to the clinic for further assessment.
- For patients with persistent grade 2-3 diarrhea, interruption of treatment may be considered to allow symptoms to improve. The TKI dose may also be reduced to control diarrhea.
- If diarrhea fails to resolve after dose reductions or discontinuation, octreotide may be considered in some cases.
- For patients with grade 4 diarrhea permanently discontinue treatment despite medical management.

MANAGEMENT OF HAND AND FOOT SYNDROME

- Hand-foot syndrome usually occurs early; and prompt initiation of management can reduce its severity and duration. Patients should be informed to keep their skin moisturized and to notify their physician of early signs of hand-foot syndrome
- For grade 1 (minimal skin changes without pain), maintain TKI dose and keep skin well hydrated.
- For grade 2 (skin changes such as peeling, blisters, bleeding, edema or hyperkeratosis, with pain that limits instrumental activities of daily living), TKI treatment may need to be interrupted in some cases. Hyperkeratosis should be controlled, the skin kept moisturized and discomfort relieved with analgesics.
- For grade 3 (skin changes such as peeling, blisters, bleeding, edema or hyperkeratosis, with pain that limits self-care activities of daily living), TKI treatment need to be interrupted. Keratosis on the pressure points of the feet can be shaved by a podiatrist; and may be reduced with topical creams with salicylic acid or urea. Other treatments directed to reduce symptoms and the impact on patient's quality of life are also recommended, including appropriate analgesics.

MANAGEMENT OF MUCOSITIS

- Before the start of treatment, patients should have an oral hygiene check-up. Patients should be advice to brush their teeth and tongue with a soft-bristled brush in addition to flossing and rinsing with normal saline.
- Patients that develop mucositis in the mouth should rinse their mouth out every two to three hours. Mouthwash or bicarbonate can be useful for grade 1 mucositis. Additionally:
- For grade 1 mucositis (minor symptomatic inflammation of the mouth) maintain TKI dose and apply triamcinolone in dental paste 2–3 times daily as needed.
- For grade 2 mucositis (causes some pain but eating and drinking are tolerable) maintain TKI dose and apply triamcinolone paste two to three times daily as needed AND oral erythromycin 250-350mg daily OR minocycline 50 mg daily. Mouthwashes that include corticosteroid are very useful for treating mouth ulcers that may develop.
- For grade 3 mucositis (severe pain that prevents them eating or drinking), temporarily discontinue TKI for 2-4 weeks. Upon improvement to grade 2 or less, reintroduce TKI at a reduced dose (see section 6.1.8 for specific details). If toxicities do not worsen, escalate the dose. If no improvement, discontinue. Apply clobetasol ointment 2–3 times daily as needed AND oral erythromycin 500 mg daily OR minocycline 100 mg daily. Mouthwashes that include corticosteroid are very useful for treating mouth ulcers; and analgesics are necessary to treat pain.

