6.1.2 FORMULATION, APPEARANCE, PACKAGING, AND LABELING

Lenvatinib is an FDA approved drug for treatment of metastatic progressive differentiated thyroid cancer. Lenvatinib capsules (Lenvima) are produced by Eisai and come in 2 strengths: 10 mg and 4 mg; capsules are supplied in cartons of 6 blister cards. Each cartoon contains a 30 day supply of Lenvatinib capsules.

Sorafenib is an FDA approved drug for treatment of metastatic progressive differentiated thyroid cancer. Sorafenib (Nexavar) is produced by Bayer in 200 mg tablets.

Cabozantinib is an FDA approved drug for treatment of metastatic progressive medullary thyroid cancer. Cabozantinib (Cometriq) is produced by Exelixis as 80 mg and 20 mg gelatin capsules.

Vandetanib is an FDA approved drug for treatment of metastatic progressive medullary thyroid cancer. Vandetanib (Caprelsa) is produced by Sanofi Genzyme in 2 strengths: 100 mg and 300 mg tablets.

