6.1.8.2 MANAGEMENT OF MOST COMMON SIDE EFFECTS SPECIFIC TO EACH TKI AGENT

Dose Reduction and Interruption Instructions for Lenvatinib

Table 1. Adverse Reactions Requiring Dose Modification of Lenvatinib

Adverse Reaction	CTCAE Grade	Action	Dose Reduce and Resume Lenvatinib
Hypertension	Grade 3 ¹	Hold	Resolves to Grade 0, 1, or 2
	Grade 4	Discontinue	Do Not Resume
Cardiac Dysfunction	Grade 3	Hold	Resolves to Grade 0, 1, or baseline
	Grade 4	Discontinue	Do Not Resume
Arterial Thrombotic Event	Any Grade	Discontinue	Do Not Resume
Hepatotoxicity	Grade 3 or 4	Hold OR Discontinue	Consider resuming at reduced dose if resolves to Grade 0-1 or baseline
Hepatic Failure	Grade 3 or 4	Discontinue	Do Not Resume
Proteinuria	Greater than or equal to 2 gm/24 hours	Hold	Resolves to less than 2 gm/24 hours
Nephrotic Syndrome	-----	Discontinue	Do Not Resume
Nausea, Vomiting, and Diarrhea ²	Grade 3	Hold	Resolves to Grade 0, 1, or baseline
Vomiting and Diarrhea ²	Grade 4	Discontinue	Do Not Resume
Renal Failure or Impairment	Grade 3 or 4	Hold OR Discontinue	Consider resuming at reduced dose if resolves to Grade 0-1 or baseline
GI Perforation	Any Grade	Discontinue	Do Not Resume
Fistula	Grade 3 or 4	Discontinue	Do Not Resume
QTc Prolongation	Greater than 500 ms	Hold	Resolves to less than 480 ms or baseline
Reversible Posterior Leukoencephalopathy syndrome	Any Grade	Hold OR Discontinue	Consider resuming at reduced dose if resolves to Grade 0 to 1
Hemorrhage	Grade 3	Hold	Resolves to Grade 0 to 1
	Grade 4	Discontinue	Do Not Resume

1: Grade 3 despite optimal anti-hypertensive therapy

2: Initiate prompt medical management for nausea, vomiting or diarrhea. Permanently discontinue for Grade 4 vomiting and diarrhea despite medical management

Other adverse reactions with Lenvatinib will be managed following the instructions from Table 2:

Table 2. Dose Modifications for Lenvatinib for treatment-related Persistent and Intolerable Grade 2 or Grade 3 Adverse Reactions or Grade 4 Laboratory Abnormalities^a

Adverse Reaction	Modification	Adjusted Dose ^b
First occurrence	Interrupt until resolved to Grade 0-1 or baseline	20 mg (two 10 mg capsules) orally once daily
Second occurrence ^c	Interrupt until resolved to Grade 0-1 or baseline	14 mg (one 10 mg capsule plus one 4 mg capsule) orally once daily

Third occurrence ^c	Interrupt until resolved to Grade 0-1 or baseline	10 mg (one 10 mg capsule) orally once daily
-------------------------------	---	---

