a: Initiate medical management for nausea, vomiting, or diarrhea prior to interruption or dose reduction of Lenvatinib

b: Reduce dose in succession based on the previous dose level (24 mg, 20 mg, or 14 mg per day)

c: Refers to the same or a different adverse reaction that requires dose modification

Patients with confirmed systolic BP ≥140 mmHg or diastolic BP ≥90 mmHg will be administered antihypertensive agents and monitored every 1-2 weeks. In patients with systolic BP ≥160 mmHg or diastolic BP ≥100 mmHg despite optimal management the treatment dose will be reduced. Patients with confirmed proteinuria Grade ≥2 (1.0–3.4 g/24h) will be tested every 2 weeks; and treatment will be interrupted until proteinuria decreases to Grade 0–1 or baseline level at which time, a lower dose will be restarted.

For patients with DTC, the recommended dose of Lenvatinib is 14 mg taken orally once daily in patients with severe renal impairment (creatinine clearance [CLcr] less than 30 mL/min calculated by the Cockcroft-Gault equation) or severe hepatic impairment (Child-Pugh C)

Dose Reduction and Interruption Instructions for Sorafenib

Temporary interruption of Sorafenib is recommended in patients undergoing major surgical procedures.

Temporary interruption or permanent discontinuation of Sorafenib may be required for the following:

- Cardiac ischemia or infarction
- Hemorrhage requiring medical intervention
- Severe or persistent hypertension despite adequate anti-hypertensive therapy
- Gastrointestinal perforation
- QTc prolongation
- Severe drug-induced liver injury

Table 3. Recommended Doses for Patients with DTC Requiring Sorafenib Dose Reduction

Dose Reduction	Sorafenib Dose	
First Dose Reduction	600 mg daily dose	400 mg and 200 mg 12 hours apart (2 tablets and 1 tablet 12 hours apart – either dose can come first)
Second Dose Reduction	400 mg daily dose	200 mg twice daily (1 tablet twice daily)
Third Dose Reduction	200 mg daily dose	200 mg once daily (1 tablet once daily)

When dose reduction is necessary for dermatologic toxicities, reduce the Sorafenib dose as indicated in Table 4 below.

Table 4. Recommended Sorafenib Dose Modifications for treatment-related Dermatologic Toxicities

Dermatologic Grade	Toxicity	Occurrence	Sorafenib Modification	Dose
--------------------	----------	------------	------------------------	------

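### The hypertension rule in Section 6.1.8.1, headed as not agent-specific, restarts any study TKI at 20, 14 or 10 mg: these are lenvatinib dose levels and fit none of the other three agents

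*Combined protocol and SAP*

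**What the plan says.** Section 6.1.8.1 carries the heading "MANAGEMENT OF MOST COMMON GENERAL SIDE EFFECTS OF TKI TREATMENT (NOT AGENT-SPECIFIC", so on its face it applies to every participant, whichever of the four TKIs is taken. Within it, the hypertension rule acts when systolic pressure of 160 mmHg or more, or diastolic pressure of 100 mmHg or more, "persists despite maximal antihypertensive therapy, then study drug administration should be interrupted and restarted at a dose of 20 mg once daily". The restart is allowed once pressure is 150/95 mmHg or below. If the high pressure recurs on 20 mg, "study drug administration should be interrupted and restarted at a dose of 14 mg once daily"; if it recurs on 14 mg, "study drug administration should be interrupted and restarted at a dose of 10 mg once daily". The rule ends with a stop, "For Grade 4 hypertension (life-threatening consequences) discontinue study drug", and a line leaving any additional reduction to the PI's judgment. None of these bullets names an agent.

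Section 6.1.8.2 then gives rules for each agent:

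- **Lenvatinib:** the first reduction in Table 2 is to "20 mg (two 10 mg capsules) orally once daily", followed by 14 mg and 10 mg, with the footnote "Reduce dose in succession based on the previous dose level (24 mg, 20 mg, or 14 mg per day".
- **Sorafenib:** Table 3 lists 600, 400 and 200 mg daily. Severe or persistent hypertension despite treatment may call for interruption or permanent discontinuation.
- **Cabozantinib:** Table 5 lists 100 mg, then 60 mg, then 60 mg if tolerated or stop. Hypertension that stays uncontrolled despite the best medical treatment is a reason for permanent discontinuation.
- **Vandetanib:** 200 mg, then 100 mg, for toxicity of Grade 3 or greater. Hypertension is not named.

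On strengths, Section 6.1.2 states that "Sorafenib (Nexavar) is produced by Bayer in 200 mg tablets". It lists cabozantinib as 80 mg and 20 mg capsules, and vandetanib as 100 mg and 300 mg tablets.

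**The concern.** A rule declared to be general contains fixed milligram doses, and those doses belong to one drug. The neighbouring rules in Section 6.1.8.1 do not do this: proteinuria and Grade 3 mucositis call only for a reduced dose. The hypertension bullets therefore look like lenvatinib text that was carried into the general section without its label.

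What is at stake is dosing safety. For sorafenib and vandetanib the order cannot be filled, so staff would have to improvise in a patient whose hypertension has just proved refractory. For cabozantinib the first step can be filled, so the wrong dose could reach the patient. Section 7.3.6 sends staff to Section 6.1.8 as a whole for dose changes, and Section 14.3 says that the protocol is to be followed as written. A physician who sensibly uses Section 6.1.8.2 instead is therefore arguably departing from an explicit instruction.

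**Working it through.** The plan gives no calculated figure to reproduce. The check compares the three restart doses with each agent's own levels and strengths.

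**Inputs**

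- Restart doses: 20, 14 and 10 mg once daily (Section 6.1.8.1).
- Starting daily doses (Section 6.1.8): lenvatinib 24 mg; sorafenib 2 × 400 = 800 mg; cabozantinib 140 mg; vandetanib 300 mg.
- Reduction levels: Section 6.1.8.2, as listed above.
- Unit strengths (Section 6.1.2): lenvatinib 10 and 4 mg; sorafenib 200 mg; cabozantinib 80 and 20 mg; vandetanib 300 and 100 mg.

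**Step 1. Is the restart dose a listed reduction level?** For lenvatinib, 20, 14 and 10 mg are all listed (3 of 3). For sorafenib, cabozantinib and vandetanib, none is listed (0 of 3 each).

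**Step 2. Can whole units make it?** For lenvatinib, 20 = 2 × 10, 14 = 10 + 4 and 10 = 1 × 10, so all three can be made. Sorafenib doses must be multiples of 200 mg and vandetanib doses multiples of 100 mg, so neither can make any of the three. Cabozantinib doses must be multiples of 20 mg, so 20 mg can be made and 14 and 10 mg cannot. Across the three non-lenvatinib agents that is 0 + 0 + 1 = 1 of 3 × 3 = 9 combinations; the other eight cannot be filled.

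**Step 3. How far off is each dose?** Percentage of start = restart dose / starting daily dose. Ratio = lowest listed reduction level / restart dose.

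| Agent | 20 mg as % of start | 14 mg | 10 mg | Lowest listed level | Ratio at 20 / 14 / 10 mg |
|---|---|---|---|---|---|
| Lenvatinib | 20/24 = 83.3 | 58.3 | 41.7 | 10 mg | 0.5 / 0.7 / 1.0 |
| Sorafenib | 20/800 = 2.5 | 1.75 | 1.25 | 200 mg | 10 / 14.3 / 20 |
| Cabozantinib | 20/140 = 14.3 | 10.0 | 7.1 | 60 mg | 3 / 4.3 / 6 |
| Vandetanib | 20/300 = 6.7 | 4.7 | 3.3 | 100 mg | 5 / 7.1 / 10 |

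The one order that can be filled, cabozantinib 20 mg, is 20/60 = one third of the Table 5 floor.

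**Step 4. Does any text rescue the rule?** Three candidates were checked. The PI-judgment line covers only reductions beyond the stated steps. The pointer to Section 6.1.8 for dose details sits in the Grade 3 mucositis rule, not in the hypertension rule. No sentence says that Section 6.1.8.2 prevails where the two sections differ.

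**The case against.** The best defence is that the correct doses are already in the protocol. A general section is paired with one headed as specific to each agent, and a clinician would naturally take dose levels from the second. The mucositis pointer shows that, at least there, the general section expects levels to be found elsewhere in 6.1.8. For sorafenib and vandetanib the error exposes itself, because the pharmacy cannot fill the order. The one order that can be filled is an under-dose, not an overdose. The drugs are approved, standard of care and used at a single site, and Section 14.3 allows immediate action for safety. All of this stands and lowers the practical risk. It does not correct the text, which still gives an explicit order for three agents and no rule of precedence. For sorafenib and vandetanib, Section 6.1.8.2 supplies no restart dose specific to hypertension, so the only explicit one is the wrong one in 6.1.8.1.

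A reader might go further and infer that the two sections flatly contradict each other on cabozantinib: permanent stop in one, restart in the other. The documents do not settle that. The 6.1.8.1 restart applies only after pressure has fallen to 150/95 mmHg or below. Whether hypertension that resolves off drug still meets the permanent-stop criterion is left open. A reader might also infer a loss of power or a distorted primary endpoint. Nothing in the documents supports a figure for either.

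**Conclusion.** The rule is wrong as written for three of the four study drugs. None of its three doses is a listed reduction level for sorafenib, cabozantinib or vandetanib, and eight of the nine orders cannot be filled. This is a drafting inconsistency with a modest practical risk. It should be corrected because it concerns dosing and the correction is cheap.

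The conclusion assumes that tablets and capsules are dispensed whole. The percentages use the standard starting doses; the lower starts for hepatic impairment (cabozantinib 80 mg) or renal impairment (vandetanib 200 mg) would change the percentages but not the finding. The 60 mg floor is that of Table 5; the separate 40 mg adjustment of cabozantinib for strong CYP3A4 inhibitors is an interaction rule and is not counted here. The number of participants on each drug and the rate of refractory hypertension are not stated, so the number who could be affected cannot be estimated.

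The cabozantinib stop-or-restart question is secondary: an ambiguity to clarify, not a demonstrated conflict.

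**What to change.** Amend the hypertension rule in Section 6.1.8.1 as follows:

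1. Label the 20, 14 and 10 mg steps as applying to lenvatinib only.
2. For sorafenib, cabozantinib and vandetanib, say: interrupt, and when blood pressure is 150/95 mmHg or below, restart at the next lower dose level in Section 6.1.8.2 (sorafenib Table 3; cabozantinib Table 5; vandetanib 200 mg, then 100 mg), unless that section requires permanent discontinuation. The 150/95 threshold needs to stay, because Section 6.1.8.2 gives no blood-pressure restart threshold for sorafenib.
3. Keep the Grade 4 hypertension stop for all four agents, and say that it overrides the vandetanib rule that allows resumption after toxicity of Grade 3 or greater.
4. Separately, ask the sponsor to state whether pressure that is uncontrolled on cabozantinib despite optimal treatment, but normalises off drug, meets the permanent-stop criterion. This is a clinical decision. It also bears on the primary endpoint, since discontinuation for intolerability is one of its components (Section 4.2.1), so the review should not dictate the answer.

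Items 1 to 3 cost a label and a few sentences in an amendment, using levels already in the protocol, with no added visits, procedures or participants. Item 4 needs a decision by the sponsor and one further sentence.

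### The hypertension restart doses in 6.1.8.1, a section headed as not agent-specific, are lenvatinib's alone; and lenvatinib proteinuria has two conflicting hold-and-resume rules

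*Combined protocol and SAP*

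**What the plan says.** **Hypertension.** Section 6.1.8.1 is headed "MANAGEMENT OF MOST COMMON GENERAL SIDE EFFECTS OF TKI TREATMENT (NOT AGENT-SPECIFIC", and its hypertension bullets refer to TKI or study drug without naming one. After a hold for high-risk blood pressure, "Once the blood pressure is controlled, study drug should be resumed as described below". What follows is a ladder of fixed doses. If systolic pressure of 160 mmHg or more, or diastolic of 100 or more, persists despite maximal antihypertensive therapy, "study drug administration should be interrupted and restarted at a dose of 20 mg once daily when BP $\leq 150/95$ mmHg". A recurrence on 20 mg leads to 14 mg. For a recurrence on 14 mg, "then study drug administration should be interrupted and restarted at a dose of 10 mg once daily", on the same blood-pressure condition.

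In 6.1.8.2, lenvatinib's Table 2 lists three successive reductions: "20 mg (two 10 mg capsules) orally once daily", "14 mg (one 10 mg capsule plus one 4 mg capsule) orally once daily" and "10 mg (one 10 mg capsule) orally once daily". The other drugs have their own reductions there:

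- sorafenib (Table 3): 600, 400, then 200 mg daily;
- cabozantinib (Table 5): 100, then 60 mg, and stop if 60 mg is not tolerated;
- vandetanib (text): 200, then 100 mg.

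The mucositis bullet in 6.1.8.1 handles the same situation differently. It fixes no dose and says "reintroduce TKI at a reduced dose (see section 6.1.8 for specific details".

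**Lenvatinib proteinuria.** Section 6.1.8.1 and Table 1 hold at 2 g/24 h or more and resume below 2 g/24 h. The lenvatinib text after Table 2 takes confirmed Grade 2 or higher, given there as 1.0–3.4 g/24 h, and keeps treatment interrupted until Grade 0–1 or baseline.

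**The concern.** Both places instruct clinic staff on how to dose a patient who has active toxicity. Section 7.3.6 sends staff to 6.1.8 for dose changes, and 6.1.8 contains both the general and the drug-specific subsections. No sentence says which one prevails. Staff who follow the general hypertension bullets for sorafenib, cabozantinib or vandetanib are given a dose that does not belong to that drug. Staff managing lenvatinib proteinuria between the two thresholds are told both to treat and not to treat. At stake are correct dosing, consistent handling of patients, and whether a given action counts as a protocol deviation.

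**Working it through.** The plan states no figure to reproduce here. The check compares dose levels and thresholds.

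**Step 1. Whose doses are they?** The 6.1.8.1 ladder is 20, 14, 10 mg. Lenvatinib's Table 2 is 20, 14, 10 mg. All three match.

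**Step 2. How far below the other drugs' levels?** Share = restart dose ÷ reference dose. Floors come from 6.1.8.2 and full daily doses from 6.1.5 (sorafenib 2 × 400 = 800 mg).

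| Drug | Toxicity floor | 20 / 14 / 10 mg as share of floor | Full daily dose | 20 / 14 / 10 mg as share of full dose |
|---|---|---|---|---|
| Sorafenib | 200 mg | 10% / 7% / 5% | 800 mg | 2.5% / 1.75% / 1.25% |
| Vandetanib | 100 mg | 20% / 14% / 10% | 300 mg | 6.7% / 4.7% / 3.3% |
| Cabozantinib | 60 mg | 33% / 23% / 17% | 140 mg | 14% / 10% / 7% |
| Lenvatinib | 10 mg (third reduction) | on its own ladder | 24 mg | 83% / 58% / 42% |

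For the three other drugs, all nine comparisons with the floor fall below 100%, from 5% to 33%.

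**Step 3. Can the doses be dispensed?** This uses the strengths in 6.1.2 and assumes whole tablets or capsules.

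- Lenvatinib (10 and 4 mg): 20 = 10 + 10; 14 = 10 + 4; 10 = 10. All three can be made.
- Sorafenib (200 mg): every step is smaller than one tablet. None can be made.
- Vandetanib (100 and 300 mg): every step is smaller than the smaller tablet. None can be made.
- Cabozantinib (80 and 20 mg): 20 = one 20 mg capsule. The 14 and 10 mg steps cannot be made.

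So only cabozantinib 20 mg can be both wrongly ordered and actually given. It is 20/60 = 33% of the Table 5 floor.

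**Step 4. Lenvatinib proteinuria.** From the grade range in the text after Table 2, Grade 0–1 means below 1.0 g/24 h.

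| 24-hour protein | 6.1.8.1 and Table 1 | Text after Table 2 |
|---|---|---|
| Below 1.0 g | stay on, or resume | stay on, or resume |
| 1.0 to <2.0 g, on drug | stay on | interrupt |
| 1.0 to <2.0 g, held | resume | stay off |
| 2.0 g or more | hold | hold |

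The rules differ over one band, at both the hold and the resume step. The allowance for a return to baseline does not remove the conflict. Exclusion criterion 4 admits a patient above 30 mg/dL on dipstick only if 24-hour protein is below 1 g, so a baseline inside the band is not expected.

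**The case against.** The best defence is that 6.1.8.2 is headed as specific to each agent, supplies usable doses, and would be consulted by any competent clinician. The sorafenib and vandetanib errors expose themselves at the pharmacy. For cabozantinib, a clinician would have to overlook a ladder that ends at 60 mg. The error also runs toward under-dosing after a hypertensive event, not overdose. Much of this stands, and it limits the practical risk. It does not make the text correct: nothing gives 6.1.8.2 precedence, the hypertension bullets lack the cross-reference that the mucositis bullet has, and the allowance for further reductions on the PI's judgment cannot raise a dose that is already too low. Nor does preferring the specific rule settle proteinuria, since Table 1 and the text after Table 2 are both lenvatinib rules in 6.1.8.2. One could read that text as setting only the testing schedule at Grade 2, which would remove the conflict over when to hold. The resume criteria would still differ.

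A reader might also infer three stronger points that the documents do not support.

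- *That 20 mg is below any cabozantinib dose the protocol allows.* Section 6.1.8.2 lowers cabozantinib by 40 mg with a strong CYP3A4 inhibitor. Read literally, 60 − 40 = 20 mg, although the worked examples stop at 60 mg. The 60 mg figure is the floor for toxicity reductions in Table 5, and the comparison here is with that floor.
- *That the cabozantinib rules contradict each other on hold versus permanent stop.* Section 6.1.8.1 allows restart only at 150/95 mmHg or below, and 6.1.8 limits a toxicity delay to 4 weeks. A patient whose pressure never comes down fits the permanent-discontinuation list. More explicit wording would help, but this is not a separate defect.
- *That the proteinuria threshold decides who restarts within the 4-week limit.* The documents give no recovery times, so this cannot be shown.

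**Conclusion.** The point holds as a drafting defect in the dosing instructions. The hypertension restart doses in 6.1.8.1 are right for lenvatinib and wrong for the other three drugs, at 5% to 33% of those drugs' toxicity floors. One of the nine wrong drug-and-dose combinations, cabozantinib 20 mg, can be dispensed. Lenvatinib proteinuria has two incompatible rules between 1.0 and just under 2.0 g/24 h. The conclusion assumes whole dosage units and takes the grade boundary from the protocol's own range. How many patients would be affected cannot be computed, because the documents give neither the drug mix nor expected rates of these events. Nothing here bears on sample size, power or the planned analysis.

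**What to change.** - In 6.1.8.1, label the 20/14/10 mg steps *lenvatinib only*.
- For the other drugs, write *restart at the next lower dose level in 6.1.8.2*, and name the source: Table 3 for sorafenib; Table 5 for cabozantinib, subject to its permanent-discontinuation list; 200 then 100 mg for vandetanib. Sorafenib needs the explicit pointer, because its text permits interruption or discontinuation for severe or persistent hypertension but gives no rule for resuming.
- Have the clinical team choose, on clinical grounds, one hold threshold and one resume threshold for lenvatinib proteinuria. Use both in 6.1.8.1, Table 1 and the text after Table 2.

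The cost is a wording-only amendment with the usual IRB review. It adds no procedures.
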